## **9.1 Statistical/Analytic Considerations**

## **9.2 Size Considerations and Power Estimates**

Due to the small sample size (n=40), results will not be powered enough to be representative of the greater population. Our goal is to examine feasibility among participants and estimate the effect size of the intervention for a future RCT.

## **9.3 Data and Safety Monitoring**

The Data and Safety Monitoring Plan (DSMP) outlined below will adhere to the protocol approved by the Single Institutional Review Board (IRB) which will oversee the study activities. A Data and Safety Monitoring Board will be established after a Notice of Award is granted.

### **9.3.1 Training on Human Subjects and Data and Safety Monitoring**

All proposed staff have participated in the Department of Health and Human Services required trainings for conduct of studies that involve human subjects and any future study staff will do so upon hiring. Training for all staff includes (but is not limited to) Protection of Human Subjects, Informed Consent, Good Clinical Practice, Quality Management, Confidentiality, and Reporting of Adverse Events. If any study staff discovers any untreated condition (e.g., onset of physical or mental health condition), they will refer participants to appropriate treatment immediately.

### **9.3.2 Data Management and Data Quality**

Columbia University will be responsible for computerized survey programming and data capture, management, and analysis. All study information will be identified through the Participant Identification Number on all forms and computerized files.

### **9.3.3 Data Monitoring**

Biweekly reports for the study sites will be created by the data manager (i.e., data monitoring is done by both Columbia University staff and Vanderbilt University staff) to review relevant app engagement data, barriers with recruitment/enrollment and retention, laboratory and medical records, compliance with the protocol, and accuracy and completeness of the records. The investigative team will schedule biweekly conference calls, and these reports will be briefly reviewed by the team at these meetings. These regular reviews will ensure close communication between the research assistants, quickly identify missing data points, and ensure consistent management of any issues with the protocol across sites. Data quality will be examined before statistical analyses are conducted, including examination of missing data, assessment of distributional assumptions, and identification of outliers. In addition to data quality, the comparability between intervention and control groups will be carefully examined, including baseline balance and differential attritions at all waves of follow-up.

## 9.3 Adverse Events

### 9.3.1 Adverse event assessment

We anticipate that the Data and Safety Monitoring Board will define study-specific serious adverse events (SAE)s. While we do not anticipate any SAEs, we will carefully review safety and data security and study drop-out.

### 9.3.2 Adverse event reporting

An **adverse event** (AE) is any symptom, sign, illness or experience that develops or worsens in severity during the course of the study. Intercurrent illnesses or injuries should be regarded as adverse events. Abnormal results of diagnostic procedures are considered to be adverse events if the abnormality:

- results in study withdrawal
- is associated with a serious adverse event
- is associated with clinical signs or symptoms
- leads to additional treatment or to further diagnostic tests
- is considered by the investigator to be of clinical significance

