# YMSM/YTGW who completed testing for HIV/syphilis at Baseline and 3-Month Follow-up
# YMSM/YTGW who self-administered the DPP® HIV-Syphilis test at Baseline and 3-Month Follow-up
# negative/positive results
# YMSM/YTGW referred for HIV/STI services (participants with HIV and/or syphilis only)
# YMSM/YTGW linked to (attend one appointment) HIV/STI prevention or care services

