### **8.3 Acquisition of HIV and/or Syphilis Infection while on Study**

If a participant receives a reactive or indeterminate result from the DPP® HIV-Syphilis test for their HIV and/or Syphilis status during the course of the study, the study team will link them to confirmatory testing on site at the clinic.

To facilitate these tasks, study staff must complete the HIV/Syphilis Confirmation Testing instrument in REDCap which should be updated with the information around the preliminary positive, confirmatory test, and linkage to care information as it is updated. Once HIV and/or syphilis status has been confirmed as positive, participants will be withdrawn from study.

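### Under Section 9.3.2 a reactive or indeterminate study test becomes an adverse event once it leads to confirmatory testing or withdrawal, and only the intervention arm has study tests

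*Combined protocol and SAP*

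**What the plan says.** Section 9.3.2 (Adverse event reporting) first defines an adverse event in general terms, limited to things that arise or get worse while the participant is on study. It then adds a rule for test findings: "Abnormal results of diagnostic procedures are considered to be adverse events if the abnormality" meets any one of five criteria. Two of them matter here: the abnormality "results in study withdrawal", or it "leads to additional treatment or to further diagnostic tests". The study's own test is not exempted.

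Section 8.3 sets out what follows a reactive or indeterminate DPP result: "the study team will link them to confirmatory testing on site at the clinic". It continues: "Once HIV and/or syphilis status has been confirmed as positive, participants will be withdrawn from study". The section also requires staff to complete a dedicated REDCap instrument covering the preliminary positive, the confirmatory test and linkage to care.

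Table 2 (Section 6.2) lists the number of "negative/positive results" among the outcome data.

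Sections 3.1 and 3.2 and Table 1 give the intervention arm a DPP test at baseline and at 3 months. Sections 3.2 and 5.3 state that controls are not offered HIV or syphilis testing.

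Section 10.6 enters all adverse events in the study database. The safety report it describes covers serious and unexpected events and other unanticipated problems, and the six-monthly DSMB review covers serious adverse events.

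**The concern.** The test is the intervention, and finding infection is part of what the study is meant to do. Under the rule as written, a detection becomes an adverse event through the steps the protocol itself prescribes, whether it is a new infection, an older one only now found, or a reactive result that confirmation does not bear out. The same positive result is then both an outcome and an adverse event.

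Because the study tests one arm only, this class of event can arise from study procedures in that arm alone. Anyone who later counts adverse events by arm from the database would see a difference that partly measures testing. Section 9.3.1 (Adverse event assessment) expects no serious adverse events, and only 40 people are enrolled. A few detections could therefore make up much of the record and make real harms of the procedure, such as lancet injury or distress after a result, harder to see.

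**Working it through.** The plan states no figure on this point, so there is none to reproduce. The check has two parts.

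**1. The rule against the procedure**

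| Event on study | Step under Section 8.3 | Criterion in Section 9.3.2 | Listed in Table 2? |
|---|---|---|---|
| Reactive DPP result | Link to confirmatory testing | Further diagnostic tests | Yes, as a positive result |
| Indeterminate DPP result | Link to confirmatory testing | Further diagnostic tests | Not named |
| Confirmed positive | Withdrawal | Study withdrawal | Yes, as a positive result |

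This treats a reactive or indeterminate result as abnormal and the DPP test as a diagnostic procedure, which is the natural reading. One criterion is enough, so the rule applies whenever the confirmatory test or the withdrawal takes place.

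**2. How many events this could produce**

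Inputs:
- Total sample 40 (Schema), allocated 1:1 (Section 3.2): nominally 40 / 2 = 20 tested participants and 20 controls without study tests.
- p, the proportion of tested participants with at least one reactive or indeterminate result: not given for this sample, so assumed. Section 1.1 cites an HIV prevalence of 5% to 20% in community samples of young trans women. Enrollees here report negative or unknown status, so that is a different population; 20% serves only as an outer value.

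Formulas: expected participants = 20p; chance of at least one = 1 − (1 − p)^20.

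| Assumed p | Expected participants | Chance of at least one |
|---|---|---|
| 2% | 20 × 0.02 = 0.4 | 1 − 0.98^20 = 0.33 |
| 5% | 20 × 0.05 = 1.0 | 1 − 0.95^20 = 0.64 |
| 10% | 20 × 0.10 = 2.0 | 1 − 0.90^20 = 0.88 |
| 20% (outer value) | 20 × 0.20 = 4.0 | 1 − 0.80^20 = 0.99 |

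In the control arm the number from study tests is 0 by design.

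The same percentages applied per test, over 20 × 2 = 40 tests, give larger figures: at 2%, 5% and 10%, 0.8, 2 and 4 events, with a 55%, 87% and 99% chance of at least one. That version treats a person's two tests as independent and ignores that a confirmed case leaves before the second test, so the per-participant figures are the safer ones.

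As a gauge of scale, 4 of 20 against 0 of 20 gives a two-sided Fisher exact p of 0.106, and 5 of 20 against 0 of 20 gives 0.047. Five or more affected participants have probability 0.003 at p = 5% and 0.04 at p = 10%.

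**The case against.** The strongest reply is that little follows from this. No table or comparison of adverse events by arm is specified, and the analysis plan in Section 9.4 concerns testing, not safety. Detections can already be identified from the REDCap confirmation instrument and Table 2, and Section 10.6 asks the safety report to state whether its events appear related to the study. Broad capture of adverse events is also a defensible choice for a test used outside its approved setting. No stated decision in a 40-person feasibility study depends on the count.

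Much of that stands, and it sets the limits of the point. A reader might infer four stronger things that the documents do not support:

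- That a planned safety table counts diagnostic yield as harm, or that the DSMB would see an excess in the intervention arm. No such table exists, and the outputs in Section 10.6 are narrower than all adverse events. Section 9.3.2 does send events unrelated to the intervention to the monitoring entity, but as event reports, not comparative rates.
- That every reactive or indeterminate result is an adverse event by definition. Section 5.4 has staff help set up a confirmatory appointment after a positive result, and it may be missed. The further-testing criterion may then not be met, although the criterion on clinical significance could still apply.
- That an infection predating enrolment certainly counts. The opening definition may exclude one found at baseline; whether it governs the later sentence on abnormal results is unclear.
- That controls cannot have infection-related adverse events. An infection diagnosed elsewhere could be recorded as an intercurrent illness.

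The reply does not remove the conflict itself. The rule contains no exemption, Section 10.6 puts all adverse events in the database, and two staff members could code the same baseline result differently. The confirmation instrument makes detections identifiable but does not say that they are not adverse events.

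**Conclusion.** The point holds as a minor one. Sections 8.3 and 9.3.2, read together, put reactive and indeterminate study-test results into the adverse-event record whenever confirmatory testing or withdrawal follows, while Table 2 treats positive results as an outcome. Study testing in one arm makes ascertainment unequal; it does not make infection-related events impossible in controls. The consequence reaches the record and any later tabulation by arm, not an analysis that the plan specifies.

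The direction follows from the design. The size does not: the illustrative 0.4 to 2 participants rests on the assumed 2% to 10%, on 20 tested participants, and on confirmatory testing or withdrawal following each such result.

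**What to change.** Reconcile Section 9.3.2 with Section 8.3 by adding one paragraph:

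- A reactive or indeterminate study-test result, and the confirmatory test or withdrawal that follows from it, is recorded as a study outcome in the existing REDCap HIV/Syphilis Confirmation Testing instrument and is not in itself an adverse event. State that this applies at both baseline and 3 months, which settles the doubt about infections found at baseline. Check that the instrument has fields for indeterminate and not-confirmed results, since Section 8.3 does not name them among its contents.
- Any harm from the test procedure or from receiving its result is still recorded as an adverse event.
- False results stay subject to the unanticipated-problem and unanticipated-device-effect rules already in Section 9.3.2.

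In the report to the DSMB, add a separate line for study-test results (reactive, indeterminate, confirmed, not confirmed), and show infections reported from any source for both arms.

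The cost is one paragraph and one addition to the safety report. The headline adverse-event count becomes less inclusive, but the same results remain visible to the DSMB. This is a recording rule only; it leaves testing, confirmation and withdrawal as they are.

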#### **Serious Adverse Event**

Adverse events are classified as serious or non-serious. A **serious adverse event** is any AE that is:

- fatal
- life-threatening
- requires or prolongs hospital stay
- results in persistent or significant disability or incapacity
- a congenital anomaly or birth defect
- an important medical event

Important medical events are those that may not be immediately life threatening but are clearly

of major clinical significance. They may jeopardize the participant's health and may require intervention to prevent one of the other serious outcomes noted above. For example, drug overdose or abuse, a seizure that did not result in in-patient hospitalization, or intensive treatment of bronchospasm in an emergency department would typically be considered serious.

All adverse events that do not meet any of the criteria for serious should be regarded as ***non-serious adverse events***.

We will follow the guidelines of the IRB that require investigators to promptly notify the IRB (within 1 week from awareness of the occurrence) when an adverse event (AE) or serious adverse event (SAE) meets the definition of an Unanticipated Problem (UP).

The IRB requires that any event that is unexpected, related or possibly related to the research intervention, and suggests that the research places subjects or others at a greater risk of harm (including physical, psychological, economic or social harm) than was previously known or recognized must be reported. Events that are unrelated to the research intervention do not have to be reported to the IRB; however, we will report these to the monitoring entity and Centers for Disease Control and Prevention (CDC). Risks that are described in the protocol and consent form do not have to be reported unless the expected event occurs more frequently or is more severe than expected. One exception to this rule is in the case of a death. All deaths must be reported whether or not the death was related to the research.

An unanticipated adverse device effect (UADE) is defined as "any serious adverse effect on health or safety or any life-threatening problem or death caused by, or associated with, a device, if that effect, problem, or death was not previously identified in nature, severity, or degree of incidence in the investigational plan or application (including a supplementary plan or application), or any other unanticipated serious problem associated with a device that relates to the rights, safety, or welfare of subjects" (In accordance with 21 CFR 812.3(s)).

In accordance with 21 CFR 812, UADEs will promptly be reported to the FDA and IRB, but no later than 10 working days after the investigator first learns of the event.

#### **9.4 Data Analysis Plan**

All multivariate analyses will be preceded by standard descriptive bivariate analyses to describe the key variables and relationships among them. These analyses will include means, frequency tables, histograms, and examination of distributions. Frequencies and rates of HIV/syphilis tests, as well as corresponding confidence intervals, will be calculated for each arm (mLab App Plus vs. Standard of Care (Control)). Logistic regression models will be used to compare in the likelihood of having HIV/STI tests between the mLab App Plus arm and the standard clinic-based testing arm.

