## **mLab App Plus SCHEMA**

Purpose:	The purpose of this research study is to assess the feasibility of the “mLab App Plus,” which provides an imaging algorithm that incorporates a duplex HIV/syphilis point-of-care (POC) test.
Design/ Evaluation:	We will conduct a randomized control feasibility trial (RCT) of participants randomized to two study arms: 1) the mLab App Plus and 2) standard of care (SOC).
Intervention:	

• mLab App Plus

• HIV/syphilis point of care test (DPP® HIV-Syphilis)

Study Duration:	This will be a 3-month study.
Population:	Men who have sex with men (MSM) and transgender women (TGW) who have sex with men ages 18-39 in New York City (NYC)
Sample Size:	40 YMSM and TGW (18-39 years)
Participating Sites:	Columbia University School of Nursing (Washington Heights, NYC)
Data Collection:	We will use self-report surveys to measure demographics, knowledge, attitudes, skills, and behaviors. We will measure testing uptake with data collected from the app and through survey collection.
Summary	MSM, especially young MSM (YMSM), and TGW have some of the highest rates of HIV and syphilis diagnoses in the United States. The goal of this proposed feasibility study is to pilot the mLab App Plus to assess YMSM’s and YTGW’s abilities to perform and interpret self-tests for HIV and syphilis and consequently increase the number of YMSM and YTGW who initiate self-testing for HIV and syphilis.

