### **3.0 STUDY DESIGN**

#### **3.1 Randomized Control Trial**

We will conduct a small-scale digital RCT to evaluate the feasibility of the mLab App Plus and testing/linkage to care uptake as compared to the control arm (receiving SOC). We will enroll 40 YMSM and YTGW (ages 18-39) who report being negative for HIV and syphilis, or whose statuses are unknown, and randomize them into the intervention or control condition. The trial includes screening, a baseline appointment, and a 3-month follow-up appointment.

**Intervention Condition:** Participants randomized to intervention will be provided with the mLab App Plus, and a box of condoms. The intervention arm will also complete two HIV/Syphilis Ab Combo Rapid Tests (DPP® HIV-Syphilis Test) at their baseline (1st test) and 3-month follow-up (2nd test) appointments in the clinic (more details in section 5.4 Intervention/Investigation Procedures).

**Control Condition:** Participants randomized to standard care will be sent an email with links to mobile-optimized online prevention information, including PrEP and HIV/STI testing information found on the CDC website, and a box of condoms .

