#### **3.2 Study Randomization**

After providing informed consent, participants will be randomized to study arms in a 1:1 ratio of intervention to control arms. To reduce opportunities for selection bias, we will use a variable permuted randomization block design where block size itself is randomly selected (i.e., blocks of four to eight). The advantage of a permuted block design is that treatment assignment is pre-determined before the trial begins and assignment remains static throughout the trial. Both groups will receive standard care HIV/STI testing-related risk reduction counseling, a box of condoms, and PrEP assessment. The intervention group will self-administer their first DPP® HIV-Syphilis Test under the supervision of a trained clinician at baseline and again at their 3-month follow-up. No control group participant will be offered HIV or Syphilis testing in order to observe intervention outcome.

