## **5.0 Study Procedures**

### **5.1 Enrollment Procedures**

After successfully providing consent, the participant will be randomized to a study arm and then complete a computer self-administered baseline survey (further described in section 5.4). After completing the baseline survey, both groups will receive standard care HIV/STI testing-related risk reduction counseling, a box of condoms, and PrEP assessment. Participants who are randomized to the intervention arm will be given a DPP® HIV-Syphilis Test at their baseline appointment, which they will self-administer in the presence of a qualified clinician.

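### Section 9.4 compares testing by arm without saying when or which tests count, although study tests are scheduled in one arm only

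*Combined protocol and SAP*

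**What the plan says.** Section 9.4 gives frequencies and rates of HIV/syphilis tests with confidence intervals by arm, then the model: "Logistic regression models will be used to compare in the likelihood of having HIV/STI tests between the mLab App Plus arm" and a control arm that it names after standard clinic-based testing. It states no period and no rule on the source of a test. It also moves from HIV/syphilis tests (rates) to HIV/STI tests (model).

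The arms differ in what the study itself supplies:

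- **Intervention.** Section 3.1: "The intervention arm will also complete two HIV/Syphilis Ab Combo Rapid Tests", at baseline and at 3 months. Section 5.1: "Participants who are randomized to the intervention arm will be given a DPP® HIV-Syphilis Test at their baseline appointment". Sections 2.1 and 5.4 let the clinician run the test if the participant cannot or prefers not to.
- **Control.** Section 3.1: "Participants randomized to standard care will be sent an email with links to mobile-optimized online prevention information", plus condoms. Section 3.2 adds counseling and a PrEP assessment for both arms, and then says: "No control group participant will be offered HIV or Syphilis testing in order to observe intervention outcome".

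Three places come near a definition:

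- Section 6.2, Table 2 counts "YMSM/YTGW who completed testing for HIV/syphilis at Baseline and 3-Month Follow-up".
- The Schema names data sources: "We will measure testing uptake with data collected from the app and through survey collection".
- Another row of Table 2 gives STI testing as one example within a composite of prevention and social service appointments.

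Section 5.4 lists testing history in the baseline survey, but only opinions about testing in the 3-month survey.

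**The concern.** Testing is both the assigned procedure in one arm and the outcome of the between-arm model. If study-visit tests count, the model mostly records that the protocol was carried out. The first of those tests takes place at the same visit as consent and randomization, before the app has had time to change behavior.

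Aim 2 in Section 1.3 seeks effect sizes for the mLab App Plus on testing uptake, and Section 9.2 wants an effect size for a future RCT. Without a label and a test-source rule, a number produced largely by scheduling could be carried forward as the app's effect on whether people seek testing. Outside tests that are not asked about at 3 months may be impossible to recover later.

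**Working it through.** **Inputs from the documents.** N = 40 (Section 9.2), allocated 1:1 (Section 3.2), so about 20 per arm. Scheduled study tests: two against none (Sections 3.1 and 3.2; Section 5.4, Table 1). The plan gives no control testing rate, effect size, alpha or power, so it has no figure to reproduce.

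**Assumed inputs.** Let *a* be the share of the intervention arm with a counted study test, taken as 0.80 to 1.00. Let *c* be the share testing outside the study, equal in both arms (no effect on outside testing), taken as 5% to 20%, with 60% as a stress case. For context, Section 1.1 cites past-year HIV testing of 10.0% in transgender women and 21.6% in cisgender gay and bisexual men. At a constant rate these are 1-(1-0.10)^0.25 = 2.6% and 1-(1-0.216)^0.25 = 5.9% per 3 months. They are HIV only and from another sample. Counseling and testing links could raise *c*.

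**Step 1: expected risk difference when study tests count.**
RD = P(study or outside test) - c = a - P(both).
If the two kinds of testing are independent, P(both) = ac and RD = a(1-c).
Without independence, RD lies between a - min(a, c) and min(a, 1-c).

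| c | a = 0.80, independent | a = 0.80, bounds | a = 0.90, independent | a = 1.00 |
|---|---|---|---|---|
| 5% | 0.76 | 0.75-0.80 | 0.855 | 0.95 |
| 10% | 0.72 | 0.70-0.80 | 0.81 | 0.90 |
| 20% | 0.64 | 0.60-0.80 | 0.72 | 0.80 |
| 60% | 0.32 | 0.20-0.40 | 0.36 | 0.40 |

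Over *c* = 5-20% the range is 0.64-0.95 under independence and 0.60-0.95 without it. At *c* = 60% it is 0.32-0.40 and 0.20-0.40.

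**Step 2: sensitivity to a real effect.** At a = 1.00, RD = 1-c whatever happens to outside testing in the intervention arm. With c = 20% it is 0.80 whether the app adds nothing or adds 20 points.

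**Step 3: the fitted model.** With 20/20 tested against 4/20, the risk difference is 0.80 (Newcombe 95% CI 0.531 to 0.919) and Fisher p = 1.5e-7, although the app is inert by assumption. The empty cell leaves the logistic model without a finite odds ratio. At a = 0.90, let p = 1-(1-a)(1-c). The chance that the intervention arm is all tested or the control arm has none tested is 1-(1-p^20)(1-(1-c)^20) = 0.45, 0.26 and 0.20 for c = 5, 10 and 20% (independence assumed).

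**Step 4: the Table 2 reading.** If only study-visit tests count, control is 0/20 by design (exact 95% CI 0 to 0.168) against up to 20/20 (0.832 to 1).

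**Step 5: the window matters.** Suppose the app raised 3-month attendance by 10 points. Under independence, an any-test outcome moves (1-b) x 0.10 x (1-c), where *b* is the share with a baseline test. That is 0 to 1 point for b = 0.90-1.00. A 3-month-only outcome moves 0.10 x (1-c) = 8 to 9.5 points for c = 5-20%.

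**The case against.** The strongest reply is that the test is part of what is being evaluated. The Schema lists "HIV/syphilis point of care test (DPP® HIV-Syphilis" under Intervention, Section 3.2 is open that controls are offered no test, and Section 9.2 speaks of the effect of the intervention. This stands. A reader might infer that the between-arm comparison is invalid, or that the plan claims an effect of the app alone. The documents support neither. If the future RCT tests the same package, the package contrast is a relevant planning quantity. What is missing is the label and a separate view of self-sought testing.

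A reader might also infer that outside testing is not measured at all. That goes too far. Table 2 has a composite that mentions STI testing, the Schema names the survey as a source on uptake, and the survey itself is not in the documents. The supportable statement is that self-sought HIV or syphilis testing is not isolated and not linked to the Section 9.4 model. Table 2 does give visit time points, but Section 9.4 does not refer to them.

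Finally, this is a feasibility pilot that disclaims power. That limits the severity. However, estimating an effect size for a later trial is a stated goal, so what the estimate measures needs defining.

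**Conclusion.** The point holds as a gap in definition and labelling that should be fixed. If study tests count, Section 9.4 yields a risk difference of about 0.60 to 0.95 with no effect on outside testing. This assumes 80-100% with a study test and 5-20% control testing; it is 0.20 to 0.40 at 60% control testing. The assumed rates set the size. The direction does not depend on them, because two scheduled tests face none. Ordinary logistic regression fails outright if every intervention participant takes the baseline test.

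The primary outcome in Section 6.2, successful self-administration, is unaffected, and the per-arm rates with confidence intervals remain estimable.

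**What to change.** 1. In Section 9.4, state the window (randomization to the 3-month visit) and define two labelled outcomes.
   - (a) Any test, including study-visit DPP tests, labelled the app-plus-test package contrast. Also report study DPP completion as a single-arm proportion with an exact interval.
   - (b) At least one HIV or syphilis test obtained outside study visits between baseline and 3 months, compared between arms. Exclude, or count separately, confirmatory tests after a reactive or indeterminate study result (Sections 5.4 and 8.3). Staff arrange these and only the intervention arm can have them.
2. In Section 5.4, confirm or add the same 3-month survey item for both arms on tests since baseline: type, date, place and reason. State how participants withdrawn after a confirmed positive (Section 8.3) are handled in (b).
3. Report risk differences with intervals valid for sparse cells, and use a penalised or exact method if a cell is zero.
4. Use one test definition throughout Section 9.4, reword the control-arm label to match Sections 3.1 and 3.2, and state that (a) is the package effect and not the app's own effect.

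**Cost.** Protocol wording and one short survey item set, with no change to visits or sample size.

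**Downsides of (b).** It is imprecise at 20 per arm: 8/20 against 4/20 gives 20 points, 95% CI -8 to +45. With an inert app, the chance of at least one arm with no outside test is 1-[1-(1-c)^20]^2 = 59%, 23% and 2% for c = 5, 10 and 20%. It appears to rest on self-report, and it may understate the effect if study testing replaces outside testing. It therefore belongs beside (a), as an estimate with its interval.
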